**Amendment Rationale:**

Safety management algorithms were updated in the Investigator Brochure, requiring revision of the Appendix 1 algorithms. This revision applies to all subjects receiving study drug, or who have discontinued study drug and are being treated for suspected pulmonary toxicity, skin toxicity and nephrotoxicity.

**Changes to the Protocol:**

1. Updated Appendix 1 Algorithm for Renal, Pulmonary and Skin to match with updated Nivolumab IB v15 and Erratum 01 to Nivolumab IB v15.

**Please maintain a copy of this amendment with your protocol. Please provide a copy to your Investigational Review Board / Ethics Committee, unless agreed otherwise with BMS.**

Table 4.3.7.1-1:	Time Windows for EORTC-QLQ-C30 Assessments	17
Table 5-1:	Observed ORR with Exact 95% CI	19
Table 7.4.1-1:	Administration of study therapy: definition of parameters.....	24
Table 10-1:	Document History.....	35

LIST OF FIGURES

Figure 2.1-1:	Study Design Schematic	8
---------------	------------------------------	---

Research Hypothesis:

Treatment with nivolumab will lead to clinical benefit, as demonstrated by an improved clinically meaningful objective response rate, including durable responses with substantial magnitude of tumor reduction in subjects with refractory FL who have failed therapy with both rituximab and an alkylating agent.

Schedule of Analyses:

The final analysis of the primary endpoint will occur at least 12 months after the last enrolled subject's first dose of study therapy. It is anticipated that accrual will last 18 months, with approximately 115 subjects enrolled (90 subjects treated). It is anticipated that the analysis of the primary endpoint will take place approximately 30 months from FPFT. Additional survival analysis will be conducted for up to 5 years beyond analysis of the primary endpoint.

2 STUDY DESCRIPTION

[figure not shown]
2.1 Study Design

This is a single-arm Phase 2 study in subjects ≥ 18 years old with relapsed FL after failure of at least two prior lines of therapy (each containing rituximab and/or an alkylating agent). Approximately 90 subjects will be treated with nivolumab 3mg/kg IV every 2 weeks.

Subjects will undergo screening evaluations to determine eligibility within 28 days prior to first dose. Each 14-day dosing period will constitute a cycle. Radiographic study evaluations will take place in accordance with [Table 2.1-1](#). A PET scan is required at baseline for all subjects, and to confirm a complete response (CR). Baseline assessments should be performed within 28 days prior to the first dose, utilizing spiral CT or MRI. An independent radiology review committee (IRRC) will also be utilized. The primary endpoint of this study is IRRC-assessed objective response rate (ORR), using revised 2007 International Working Group (IWG) Criteria for Malignant Lymphoma criteria. Secondary endpoints include IRRC-assessed duration of response (DOR), as well as complete remission rate (CRR) and PFS as determined by IRRC assessment and ORR based on investigator assessment.

The study design schematic is presented in Figure 2.1-1

Figure 2.1-1: Study Design Schematic

Time On Study	Assessment Frequency	Assessment Week (day 1 of week shown)	Assessment Window
Dose 1 to 8 Months	Every 8 weeks	9, 17, 25, 33	± 1 week
Month 9 to 2 Years	Every 12 weeks	45, 57, 69, 81, 93	± 2 weeks
> 2 Years	Every 6 months	119, 145, 171+	± 3 weeks

Note: Once subjects discontinue study therapy by proceeding to allogeneic SCT or ASCT, they will not undergo radiographic assessments as per the frequency described here, but will be followed using the following schedule. Tumor assessment (CR or non-CR) will be assessed by the investigator according to the 2007 IWG criteria and will be required on Day 100, at 6 months, 1 year and every year thereafter from the date of stem cell infusion until the first non-CR after SCT is documented.

2.2 Treatment Assignment

After the subject's initial eligibility is established and informed consent has been obtained, the subject must be enrolled into the study by calling an interactive voice response system (IVRS) to obtain the subject number. Every subject that signs the informed consent form must be assigned a subject number in IVRS. Since this is a single arm study, all enrolled subjects who meet eligibility criteria will be treated with nivolumab at 3mg/kg IV every 2 weeks.

2.3 Blinding and Unblinding

Not applicable

2.4 Protocol Amendments

This SAP incorporates the following protocol amendments.

Table 2.4-1: Protocol Amendments

Amendments	Date of Issue	Summary of Major Changes
Revised Protocol Number: 03 Incorporates amendment 04	21-JUL-2016	Update of Annex 1 of Protocol Algorithm for safety Management
Revised Protocol Number: 02 Incorporates amendment 03	23-JUL-2014	Removes the interim analyses and extends the duration of follow-up required for all subjects prior to performing the final analysis of the primary endpoint. Modifies a few eligibility criteria to facilitate enrollment.

Table 2.4-1: Protocol Amendments

Amendments	Date of Issue	Summary of Major Changes
		
Allows for continued treatment of subjects in certain instances where protocol-defined progression criteria have been met.
 
The amendment also serves to clarify various protocol requirements to ensure consistency in the execution of the study including secondary and exploratory objectives,
 
[REDACTED]

Revised Protocol Number: 01 Incorporates amendment(s) 02 and administrative letter 01
	
06-Dec-2013
	
Per FDA mandatory recommendation: Exclusion criteria have been added to exclude the following subjects
 
Subjects that have received chest radiation \leq 24 weeks prior to first dose of the study drug
 
Additional updates were also made to the protocol including items such as correcting typographical and formatting errors, including errors in the biomarker sampling schedule in Table 5.6-1

Original Protocol
	
04-Oct-2013
	
Not applicable

2.5 Data Monitoring and Other External Committees

An IRRC will be utilized in this study for determination of IRRC-assessed primary (ORR) and secondary (DOR, CRR, PFS) endpoints. The IRRC will review all available tumor assessment scans for all treated subjects. Details of IRRC responsibilities and procedures will be specified in the IRRC charter.

There will be no data monitoring committee for this study.

3 OBJECTIVES

3.1 Primary objective

To assess the clinical benefit of nivolumab, as measured by independent radiologic review committee (IRRC) assessed objective response rate (ORR) in subjects with FL who have failed therapy with both rituximab and an alkylating agent.

3.2 Secondary objectives

- To assess the duration of response (DOR) based on IRRC assessments
- To assess the complete remission rate (CRR) and the duration of CR based on IRRC assessment

- To assess the partial remission (PR) rate and the duration of PR based on IRRC assessment
- To assess progression free survival (PFS) based on IRRC assessment
- To assess the objective response rate (ORR), based on investigator assessments

3.3 Exploratory Objectives

[REDACTED]

4 ENDPOINTS

4.1 Primary endpoint ORR (IRRC-assessed)

The primary objective will be measured by the primary endpoint of IRRC-assessed ORR. It is defined as the number of subjects with a best overall response (BOR) of CR or PR, according to the 2007 IWG criteria (see [Table 4.1-1](#)), divided by the number of treated subjects. The final analysis of the primary endpoint will occur at least 12 months after the last enrolled subject's first dose of study therapy. The BOR is defined as the best response designation recorded between the date of first dose and the date of initial objectively documented progression per the 2007 IWG criteria or the first subsequent therapy date per IRRC, whichever occurs first.

The first subsequent therapy date per IRRC is determined by the IRRC based on non-palliative radiotherapy, local tumor treatment, systemic anti-cancer therapy and Stem Cell Transplant with a start date on or after the first study therapy date.

For subjects without documented progression or subsequent therapy, all available response designations will contribute to the BOR determination. For purposes of analysis, if a subject receives one dose and discontinues the study without assessment or receives subsequent therapy prior to assessment, this subject will be counted in the denominator (as non-responder).

The IRRC-assessed objective response will be further characterized by the time to response (TTR). TTR is defined as the time from first dosing date to the date of the first response (PR or CR), as assessed by the IRRC.

Table 4.1-1: 2007 IWG Response Criteria for Malignant Lymphoma

Response	Definition	Nodal masses	Spleen, Liver	Bone marrow
CR	Disappearance of all evidence of disease	(a) FDG-avid or PET positive prior to therapy; residual mass of any size permitted if PET negative (b) Variably FDG-avid or PET negative; regression to normal size on CT	Not palpable, nodules disappeared	Infiltrate cleared on repeat biopsy; if indeterminate by morphology, immunohistochemistry should be negative
PR	Regression of measurable disease and no new sites	≥ 50% decrease in SPD of up to 6 largest dominant masses (index lesions); no increase in size of other nodes (non-index lesions) (a) FDG-avid or PET positive prior to therapy; one or more PET positive at previously involved site (b) Variably FDG-avid or PET negative; regression on CT	≥ 50% decrease in SPD of nodules (for single nodule in greatest transverse diameter); no increase in size of liver or spleen	Irrelevant if positive prior to therapy; cell type should be specified
SD	Failure to attain CR/PR or PD	(a) FDG-avid or PET positive prior to therapy; PET positive at prior sites of disease and no new sites on CT or PET (b) Variably FDG-avid or PET negative; no change in size of previous lesions on CT	N/A	N/A
Relapsed disease or PD	Any new lesion or increase by ≥ 50% of previously involved sites from nadir	Appearance of a new lesion(s) > 1.5 cm in any axis, ≥ 50% increase in SPD of more than one node (index lesions), or ≥ 50% increase in longest diameter of a previously identified node > 1cm in short axis. Lesions PET positive if FDG-avid lymphoma or PET positive prior to therapy	> 50% increase from nadir in the SPD of any previous lesions	New or recurrent involvement

Key: CR = complete remission CT = computed tomography; FDG = [18F] fluorodeoxyglucose; IWG = International Working Group; NA = Not applicable; PD = progressive disease; PET = positron-emission tomography; PR = partial remission; SD = stable disease; SPD = sum of the product of the diameters

4.2 Secondary Endpoints

4.2.1 Duration of Response (IRRC-assessed)

Duration of response (DOR) is defined as the time from first response (CR or PR) to the date of initial objectively documented progression as determined using the 2007 revised International

Working Group Criteria for Malignant Lymphoma or death due to any cause, whichever occurs first. For subjects who neither progress nor die, the DOR will be censored on the date of their last evaluable tumor assessment. Subjects who start subsequent therapy without a prior reported progression will be censored at the last evaluable tumor assessments prior to or on the first subsequent therapy date per IRRC. This endpoint will only be evaluated in subjects with objective response of CR or PR. Ongoing responders are defined as responders who did not progress, did not die, are not off study and did not started a subsequent therapy.

Duration of Stable Disease will also be evaluated for subjects with SD as best response. Duration of SD is defined as the time between the first dose date to the date of the first documented progression, as determined by IRRC, or death due to any cause, whichever occurs first. Subjects who neither progress nor die will be censored at the same time they will be censored for the DOR analysis.

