4.2.2 Complete Remission Rate and Duration (IRRC-assessed)

The complete remission rate (CRR) is defined as the number of subjects with a BOR of CR according to the 2007 revised International Working Group Criteria for Malignant Lymphoma, based on IRRC assessment, divided by the number of treated subjects.

To further characterize CRR, the duration of CR will also be evaluated in subjects with objective response of CR. Duration of CR is defined as the time from first documentation of CR (the date of first negative FDG-PET scan or the date of first documentation of no disease involvement in the bone marrow (if required), whichever occurs later) to the date of initial objectively documented progression as determined using the 2007 IWG criteria or death due to any cause, whichever occurs first. Censoring will be applied as per DOR definition.

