4.2.4 Progression Free Survival (IRRC-assessed)

Progression free survival (PFS) is defined as the time from first dosing date to the date of the first documented progression, as determined by an IRRC according to the 2007 revised International Working Group Criteria for Malignant Lymphoma, or death due to any cause, whichever occurs first.

- Subjects who have no baseline tumor assessment will be censored at their first dosing date.

- Subjects who have baseline tumor assessment and who die without a reported progression will be considered to have progressed on the date of their death.
- Subjects who did not progress or die will be considered as not progressed and will be censored on the date of their last assessment.
- Subjects who did not have any on study assessments and did not die will be censored on the first dosing date.
- Subjects who started any subsequent anti-cancer therapy without a prior reported progression will be censored at the last assessment prior to or on their first subsequent therapy date.

Table 4.2.4-1: Censoring scheme used in primary analysis of PFS

Situation	Date of Progression or Censoring	Outcome
No baseline tumor assessments	First Dosing date	Not Progressed
No on study tumor assessments and no death	First Dosing date	Not Progressed
No progression per 2007 IWG criteria and no new anti-cancer treatment started	Date of last tumor assessment with no documented progression per the 2007 IWG criteria	Not Progressed
New anticancer treatment started without a prior reported progression per 2007 IWG criteria	Date of last tumor assessment prior or on the date of initiation of the subsequent anti-cancer therapy	Not Progressed
Progression per 2007 IWG criteria documented between scheduled visits or at scheduled visit without prior new anticancer treatment started	Date of the first documented tumor progression per the 2007 IWG criteria	Progressed
Death without progression per 2007 IWG criteria and without prior new anticancer treatment started	Date of death	Progressed

To further characterize PFS, progression by response to most recent prior systemic cancer therapy and progression by number of prior systemic cancer therapy lines may also be evaluated.

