7.5.2 Secondary Endpoint of Duration of Response (IRRC-assessed)

The DOR will be summarized for subjects who achieve PR or CR as determined by IRRC using KM product-limit method. Two-sided, 95% confidence intervals for median DOR will be constructed based on log-log transformation. Range of duration of response and the number of ongoing responders will also be presented. In addition, the percentage of responders still in response at different time points (3, 6 and 12 months) will be presented based on the DOR KM plot.

The status of subjects who are censored in the duration of response analysis will be tabulated using the following categories:

- received subsequent anti-cancer therapy
- off-study (with reason)

Duration of stable disease will also be estimated using KM product-limit method for subjects with SD as best response. Two-sided, 95% confidence intervals for median duration of SD will be computed.

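### The censoring sentence for duration of stable disease (SAP 4.2.1) omits new therapy before progression: read literally, whether such a subject is censored depends on whether he or she later dies

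*SAP*

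**What the plan says.** SAP 4.2.1 defines two durations.

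- **DOR** has two separate censoring sentences. The first is for subjects without an event: "For subjects who neither progress nor die, the DOR will be censored on the date of their last evaluable tumor assessment". The second is for new therapy: "Subjects who start subsequent therapy without a prior reported progression will be censored at the last evaluable tumor assessments prior to or on the first". That sentence ends by naming the start date of later treatment, as set by the IRRC. The population is restricted: "This endpoint will only be evaluated in subjects with objective response of CR or PR".
- **Duration of SD** has this definition: "Duration of SD is defined as the time between the first dose date to the date of the first documented progression, as determined by IRRC". Death from any cause, if earlier, also ends it. It has one censoring sentence: "Subjects who neither progress nor die will be censored at the same time they will be censored for the DOR analysis".

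The neighbouring endpoints all deal with new therapy.

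- Duration of CR (SAP 4.2.2) takes over the whole DOR rule: "Censoring will be applied as per DOR definition". SAP 4.2.3 does the same for duration of PR.
- PFS (SAP 4.2.4, Table 4.2.4-1) has a row for "New anticancer treatment started without a prior reported progression per 2007 IWG criteria", which censors at the last tumor assessment up to the start of that therapy. Its death row counts a death only if no new treatment came first.

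SAP 7.5.2 gives the method ("Duration of stable disease will also be estimated using KM product-limit method for subjects with SD as best response") and adds no censoring rule.

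**The concern.** The SD sentence repeats the first DOR condition and leaves out the second. A subject with SD as best response who starts another treatment before progression, and then dies, is not among those who neither progress nor die. On the words alone that subject is an event on the date of death, and the time on the next treatment is part of the recorded duration of SD.

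A subject with the same history but no later event does fall under the sentence and, through the pointer to DOR, is censored before the new therapy. Whether new therapy censors is then settled by what happens afterwards. Kaplan-Meier estimation needs censoring that does not look into the future.

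The situation can arise. Protocol 3.1 (Follow-up) continues scans after treatment stops for reasons other than progression or transplant, and follows survival every 3 months until death. The best-response window in SAP 4.1 closes at first subsequent therapy, so SD status would be judged on data up to that date while its duration ran past it.

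At stake are the interpretability of one supportive curve and a choice left to the programmer.

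**Working it through.** **1. The plan's own figure.** The documents state no number for duration of SD. The only stated operating characteristic is the power of about 87% for ORR (SAP 5; the rule of at least 27 responders in 90 is in Protocol 8.4.2.1). Exact binomial: P(X ≥ 27 | n = 90, p = 0.35) = 0.866. This agrees, and the SD censoring rule does not enter it.

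**2. The rules side by side, for a subject who starts new therapy without prior progression.**

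| Endpoint | Later death | No later event |
|---|---|---|
| DOR (SAP 4.2.1) | censored before or at therapy start | same |
| Duration of CR, PR (4.2.2, 4.2.3) | as DOR | as DOR |
| PFS (4.2.4, Table 4.2.4-1) | censored before or at therapy start | same |
| Duration of SD (4.2.1), literal | **event at death** | censored as for DOR |

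PFS and duration of SD share the same start (first dose) and the same event types, so the difference in the second column has no rationale in the definitions.

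**3. One worked record (assumed dates).** First dose is day 1, last scan day 169 (day 1 of Week 25), new therapy about day 180, death day 700. SAP 8 counts last date − first date + 1, with 30.4375 days per month.

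- Literal SD rule: 700 / 30.4375 = 23.0 months, event.
- DOR-type or PFS rule: 169 / 30.4375 = 5.6 months, censored.
- Same subject alive and progression-free at cutoff: 5.6 months, censored, under both rules.

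**4. Effect on the curve.** These inputs are assumptions, except that follow-up of 12-30 months follows from 18 months of accrual plus at least 12 months after the last first dose (SAP, Schedule of Analyses):

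- median time to progression or death on nivolumab: 8 or 12 months, exponential;
- share of SD subjects moving to new therapy first: 15%, 25% or 35%;
- median time from new therapy to the later event: 9 or 18 months, exponential;
- follow-up uniform over 12-30 months.

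The consistent rule censors everyone at the start of new therapy. The literal rule scores an event at the late date if it falls within follow-up, and otherwise censors at therapy start. For simplicity, the simulation censors at therapy start instead of at the preceding scan.

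| Progression median | Fall in 12-month rate | Fall in median |
|---|---|---|
| 8 months | about 0.4-2.9 points | 0-0.3 month |
| 12 months | about 0.7-4.3 points | 0.2-1.2 months |

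Across both, about 4-21% of SD subjects change from censored to late event, on average roughly 6-8 months after new therapy began. If 30 subjects had SD as best response (an assumption), that is 0.04 × 30 = 1.2 to 0.21 × 30 = 6.3 subjects.

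A wider grid (12-month median, 10-40% moving to new therapy, post-therapy median 6-36 months) gives medians of 10.1-11.9 months against 12.0 under the consistent rule.

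**5. Why the curve falls.** After new therapy, only subjects who go on to have an event stay in the risk set; event-free counterparts are removed at therapy start. That raises the estimated hazard, and this outweighs the longer times of the late events.

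**The case against.** The best defence is that the sentence was meant to import DOR censoring in full. SD subjects are not in the DOR analysis, so the pointer makes sense only as shorthand for the DOR rules, and those include the new-therapy rule. The SAP is loose in the same way elsewhere: the PFS bullet on death carries no new-therapy exception, and a later bullet and Table 4.2.4-1 supply it.

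Much of this stands. Full import may well have been intended, so it would be too strong to say that the SAP knowingly prescribes outcome-dependent censoring. But the sentence is limited to subjects without an event, nothing in SAP 7.5.2 or elsewhere completes it as the table does for PFS, and SAP 4.2.2 and 4.2.3 use different, complete wording when the whole rule is wanted.

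Two further limits also stand.

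- The later-progression route is less certain than the death route. After transplant there are no IRRC radiographic assessments (Protocol 5.4). After other new therapy, whether the IRRC still assigns progression may depend on a charter that was not supplied.
- A reader might infer that the report will show conflicting tables for the same subjects. The visible plan does not support that: the PFS breakdowns in SAP 7.5.5 are by response to prior therapy and number of prior lines, not by best response. The discrepancy would be seen at subject level.

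**Conclusion.** The gap is real and minor. As written, duration of SD has no rule for a subject who starts new therapy without progression and later has an event, and the literal reading is inconsistent with DOR, duration of CR and PR, and PFS.

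A reader might infer that counting time on the next therapy flatters nivolumab. The calculation does not support that. Individual durations can be much too long, but the aggregate moves slightly down: 0-1.2 months on the median and about 0.4-4.3 points on the 12-month rate. These sizes rest on assumed rates, since the documents give none, and they depend mainly on the share who switch therapy, on how soon later events follow and on the progression median.

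Duration of SD is not among the listed primary or secondary objectives and carries no test or threshold. ORR, the CR and PR rates, DOR, PFS and the 87% power do not change.

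**What to change.** In SAP 4.2.1, replace the SD censoring sentence with the wording already used for duration of CR and PR: "Censoring will be applied as per DOR definition". Add that, for duration of SD, this includes censoring at the last evaluable tumor assessment on or before the first subsequent therapy date per IRRC, whatever happens to the subject later.

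The cost is one sentence. No new data are needed, because the DOR and PFS analyses already use the subsequent-therapy date and the assessment dates. Relative to the literal rule, the duration-of-SD curve will have fewer events.
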